9.2 Recording of Adverse Events

Although AEs are not expected, should any non-serious or serious AEs occur, it is recommended that the participant seek immediate treatment. All AEs occurring during the study period must be recorded. The clinical course of each event should be followed until resolution, stabilization, or until it has been determined that the study treatment or participation is not the cause. SAEs that are still ongoing at the end of the study period must be followed up to determine the final outcome. Any SAE that occurs after the study period and is considered to be possibly related to the study treatment or study participation should be recorded and reported to the IRB immediately.

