Across both studies, there were no significant differences between the 1,3-butanediol and placebo phases on the time to complete the time trial, and the magnitudes of the effect sizes observed were interpreted as “unclear”. Similarly, no significant differences between phases were observed for power output (Shaw *et al.*, 2019) and pacing (Scott *et al.*, 2019) during the time trial; the magnitudes of the effects were interpreted as “unclear” or “very likely trivial” (for pacing for the first 3-km of the 5-km time trial). Thus, the consumption of 1,3-butanediol compared to placebo did not result in statistically significant or clinically significant improvements in time trial performance. Additionally, the consumption of 1,3-butanediol compared to placebo significantly increased blood BHB levels throughout exercise. However, the consumption of 1,3-butanediol compared to placebo did not result in statistically or clinically significant, sustained improvements in supportive outcomes of exercise performance. Furthermore, the evidence to support an effect of 1,3-butanediol on the sparing of glucose reserves is unclear. It should be noted that, in the study by Scott *et al.* (2019), BHB was elevated following administration of 1,3-butanediol but was not sufficient to induce moderate or high levels of ketosis.

In the study by Shaw *et al.* (2019), there was no difference in the change of body mass (corrected for fluid intake) between trials. Within the group consuming butanediol, two participants experienced low levels of nausea, euphoria, dizziness. Five participants reported low to moderate levels of belching and burping, and one participant reported severe abdominal pain. All participants reported that they disliked the taste of butanediol, which resulted in retching in four participants. In the study by Scott *et al.* (2019), no adverse GI effects were reported.

It should be noted that, in the study by Shaw *et al.* (2019), a pilot test was conducted prior to the primary study to determine a testing dose of 1,3-butanediol in a beverage that was well tolerated and would provide optimal BHB blood concentration. In the pilot test, single bolus doses of 0.5 g/kg and 0.7 g/kg of 1,3-butanediol resulted in nausea, euphoria, and dizziness. To resolve these issues, the authors determined a split dose of 0.35 g/kg (providing about 24.5 g/dose for a 70-kg individual) at the initiation of

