9.1 Definitions

Unanticipated Problems Involving Risk to Subjects or Others

Any incident, experience, or outcome that meets all of the following criteria:

- Unexpected in nature, severity, or frequency [*i.e.*, not described in study-related documents such as the Institutional Review Board (IRB)-approved protocol or consent form];
- Related or possibly related to participation in the research (*i.e.*, possibly related means there is a reasonable possibility that the incident, experience, or outcome may have been caused by the procedures involved in the research); and
- Suggests that the research places subjects or others at greater risk of harm (including physical, psychological, economic, or social harm).

Serious Adverse Event

AEs are classified as serious or non-serious. A serious adverse event (**SAE**) is any AE that is:

- fatal
- life-threatening
- requires or prolongs hospital stay
- results in persistent or significant disability or incapacity
- a congenital anomaly or birth defect

- an important medical event

Important medical events are those that may not be immediately life-threatening, but are clearly of major clinical significance. They may jeopardize the subject, and may require intervention to prevent one of the other serious outcomes noted above. For example, a seizure that did not result in in-patient hospitalization, or intensive treatment of bronchospasm in an emergency department would typically be considered serious.

All AEs that do not meet any of the criteria for serious should be regarded as **non-serious AEs**.

Adverse Event Reporting Period

The study period during which AEs must be reported is normally defined as the period from the initiation of any study procedures to the end of the study treatment follow-up. For this study, the study treatment follow-up is defined as the evening of the day on which the clinical study takes place.

Pre-existing Condition

A pre-existing condition is one that is present at the start of the study. A pre-existing condition should be recorded as an AE if the frequency, intensity, or the character of the condition worsens during the study period.

General Physical Examination Findings

As the study product is a food ingredient that is GRAS in the U.S., there are no general examinations planned for this clinical study.

Post-study Adverse Event

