9.3 Reporting of Serious AEs and Unanticipated Problems

The Investigator must conform to the AE reporting timelines, formats and requirements of the various entities to which they are responsible, but at a minimum those events that must be reported are those that are:

- related to study participation,
- unexpected, and
- serious or involve risks to subjects or others
- (see definitions, section 9.1).

If the report is supplied as a narrative, the minimum necessary information to be provided at the time of the initial report includes:

- Subject number
- A description of the event
- Date of onset
- Current status
- Whether study treatment was discontinued
- The reason why the event is classified as serious
- An assessment of the association between the event and study treatment by a qualified person, as needed

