9.3.1 Investigator reporting: Notifying the IRB

Investigators are responsible for safety reporting to their local IRB. Investigators are responsible for complying with their local IRB's reporting requirements, though must submit the required reports to their IRB no later than 10 working days. Copies of each report and documentation of IRB notification and receipt will be kept in the investigator's study file.

10 Study Administration, Data Handling and Record Keeping

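### The protocol's own IRB reporting rule is looser and slower for an SAE on the test day than for the same SAE after that evening

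*Combined protocol and SAP*

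**What the plan says.** Four parts of section 9 bear on when an SAE reaches the IRB.

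- **9.1 Definitions** fixes the end of the reporting period: "the study treatment follow-up is defined as the evening of the day on which the clinical study takes place". It also defines an unanticipated problem, whose first criterion is "Unexpected in nature, severity, or frequency", judged against study documents such as the protocol and consent form.
- **9.2 Recording of Adverse Events** requires AEs in the study period to be recorded and followed, and gives no IRB deadline for them. For later events it goes further: an SAE judged possibly related to the product or to taking part "should be recorded and reported to the IRB immediately". The same section opens with "Although AEs are not expected".
- **9.3 Reporting of Serious AEs and Unanticipated Problems** ties the investigator to the requirements of the bodies to which they answer. It then sets a floor: "at a minimum those events that must be reported are those that are" related to participation, unexpected, and serious or involving risk. It refers back to 9.1 for definitions.
- **9.3.1** makes the investigator follow the local IRB's rules and adds that they "must submit the required reports to their IRB no later than 10 working days". It does not say from what day the 10 working days run.

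Section 5.1 enrols participants in groups of 10. It gives no interval between groups and describes no safety review or hold between them.

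**The concern.** One would expect the tightest reporting rule to cover the hours just after dosing, when a product-related event is most plausible. Here the explicit requirement for immediate notification, free of any expectedness test, applies only once the test day is over. A serious event a few hours after the third serving, which is taken at 60 minutes, is governed by a rule with an extra condition and a longer limit than the same event the next morning.

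This matters more than it would in a clinic-based study. Participants take the product at home (4.2), there is no study monitoring (11.1), and nothing in the protocol pauses enrolment between groups. Prompt IRB notification is therefore one of the few external safeguards that the protocol contains. If it is slow, later groups could take the product before the IRB has heard of the event.

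**Working it through.** **Step 1. Set the rules side by side for one SAE.**

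| | SAE up to the evening of the test day | SAE after that evening |
|---|---|---|
| Governing text | 9.3 and 9.3.1 (9.2 asks only for recording and follow-up) | 9.2, in addition to 9.3 and 9.3.1 |
| Relatedness | Related (9.3), read with 9.1, which includes possibly related | Possibly related |
| Expectedness | Must be unexpected to fall within the stated minimum | No condition |
| Deadline | At most 10 working days | Immediately |
| Start of clock | Not stated | Not needed |

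The two columns differ on expectedness and on deadline. The relatedness wording also differs, but the reference to 9.1 largely closes that gap. No other section gives a faster deadline for a test-day SAE. The hospitalisation paragraph in 9.1 says that such events are to be reported as SAEs, but names no recipient and no time limit.

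**Step 2. Convert the deadline.** The input is 10 working days (9.3.1). Counting Monday to Friday with no holidays, 10 working days from any weekday is 2 weeks = 14 calendar days. From a Saturday it is 13, and from a Sunday 12.

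**Step 3. Count who could be dosed in that time.** The inputs are 30 participants (4.2) and groups of 10 (5.1), so 30 / 10 = 3 groups. After group 1, 2 × 10 = 20 participants remain.

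The interval between groups, g days, is not in the documents and has to be assumed. Take an SAE in group 1, a clock that starts on that group's test day, and each group tested on a single day. Then

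further participants dosed by day 14 = 10 × min(2, floor(14 / g)).

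| Assumed interval g | floor(14 / g) | Further participants dosed |
|---|---|---|
| 7 days or less | 2 or more | 20 |
| 8 to 14 days | 1 | 10 |
| over 14 days | 0 | 0 |

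If the SAE arises in group 2, only 10 participants remain, so the maximum is 10. In group 3 it is 0. A clock that starts later than the test day would lengthen the window.

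**Step 4. Ask how much the expectedness condition matters.** Section 1.4 reports that in an earlier exercise study "one participant reported severe abdominal pain", along with nausea, dizziness and retching in others. Those reactions are therefore described in the protocol. But an event can be unexpected by severity or frequency as well as by nature (9.1), and 9.2 states that AEs are not expected. Most SAEs would qualify as unexpected. The practical gap is mainly one of timing.

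**The case against.** The strongest reply is that the sections do not conflict. Section 9.3 is a general rule, not one confined to the test day, and 9.2 adds a clause for events that fall outside the reporting period. An investigator can comply with both. The 9.3 list is a minimum, the local IRB's rules bind as well, and an outer limit of 10 working days does not stop anyone from reporting the same day. All of this stands. It does not remove the difference in what the protocol itself requires, and the IRB rules that might close the gap are not in the documents.

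Four stronger readings are tempting and not supported:

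- *A test-day SAE is reportable only if unexpected.* The text sets a floor and defers to other bodies' requirements, so the word only cannot be established.
- *A related hospitalisation for abdominal pain could be classed as expected and go unreported.* Section 9.1 has hospitalisations reported as SAEs whatever their expectedness. Section 1.4 mentions no hospitalisation, so such a case would exceed the severity described there.
- *Another one or two groups will be dosed before the IRB hears.* This would follow from dividing 14 days by the 7-day screening window in Table 5.1-1. That window is a maximum for one participant, not the spacing of groups.
- *Only the IRB could act in time.* The Study Summary makes the principal investigator responsible for participant safety. Section 4.6.1 provides for removal of subjects by the investigator and for termination by the sponsor. Neither has to wait for an IRB report.

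**Conclusion.** The point holds as an inconsistency between 9.2 and 9.3/9.3.1. The same SAE meets a different trigger and a different deadline depending on which side of the test-day evening it falls, and the looser protocol rule applies closest to dosing. The missing start of the 10-working-day clock is a separate gap in 9.3.1.

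The stated difference in timing is immediate notification against as much as about 14 calendar days. Its consequence for later participants ranges from 0 to 20 of the 30 and rests wholly on an assumed interval between groups. The documents neither establish nor exclude further dosing in that time. The difference in expectedness is real on paper but probably small in practice. Actual reporting may be faster if the local IRB demands it. This is an inexpensive improvement to participant protection, not evidence that events would be concealed.

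**What to change.** Reconcile 9.2, 9.3 and 9.3.1 so that one rule covers SAEs in both periods:

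1. Extend the existing 9.2 trigger (possibly related, no expectedness condition) and its immediate timing to SAEs during the study period.
2. Keep the 10-working-day limit for other reportable events, and state that it runs from the day the investigator becomes aware of the event.

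The 9.2 remark that AEs are not expected should not be replaced by a list of the reactions in 1.4. That would make those reactions easier to class as expected under the 9.3 test, which would still govern other reportable events, and it is not needed to resolve the timing.

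The cost is a short change of wording in three sections and possibly one or two more expedited IRB reports in a 30-person study. No assessment, visit or data item changes.

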9.3 Reporting of Serious AEs and Unanticipated Problems

The Investigator must conform to the AE reporting timelines, formats and requirements of the various entities to which they are responsible, but at a minimum those events that must be reported are those that are:

- related to study participation,
- unexpected, and
- serious or involve risks to subjects or others
- (see definitions, section 9.1).

If the report is supplied as a narrative, the minimum necessary information to be provided at the time of the initial report includes:

- Subject number
- A description of the event
- Date of onset
- Current status
- Whether study treatment was discontinued
- The reason why the event is classified as serious
- An assessment of the association between the event and study treatment by a qualified person, as needed

9.3.1 Investigator reporting: Notifying the IRB

Investigators are responsible for safety reporting to their local IRB. Investigators are responsible for complying with their local IRB's reporting requirements, though must submit the required reports to their IRB no later than 10 working days. Copies of each report and documentation of IRB notification and receipt will be kept in the investigator's study file.

10 Study Administration, Data Handling and Record Keeping

10.1 Confidentiality

Information about study subjects will be kept confidential and managed according to the requirements of the Health Insurance Portability and Accountability Act of 1996 (HIPAA). Those regulations require a signed subject authorization informing the subject of the following:

- What protected health information (PHI) will be collected from subjects in this study
- Who will have access to that information and why
- Who will use or disclose that information
- The rights of a research subject to revoke their authorization for use of their PHI

In the event that a subject revokes authorization to collect or use PHI, the investigator, by regulation, retains the ability to use all information collected prior to the revocation of subject authorization.

10.2 Source Documents

Source data is all information, original records of clinical findings, observations, or other activities in a clinical trial necessary for the reconstruction and evaluation of the trial. Source data are contained in source documents. In the case of the clinical trial proposed herein, examples of original documents and data records include: consent forms and the online study portal data (blood BHB levels and questionnaires).

10.3 Records Retention

Genomatica will retain records for this clinical trial for a period of 2 years from completion of the trial, defined as the day the final subject completes the study. The files will be stored with Human Resource/Legal/Finance files – locked with restricted access; at [name].

11 Study Monitoring, Auditing, and Inspecting

11.1 Study Monitoring Plans

The clinical study described herein is a pilot study intended to determine the level of ketosis (BHB) achievable with consumption of the food ingredient, (*R*)-1,3-Butanediol. The study is not being conducted in accordance with Good Clinical Practice, and therefore, there is no clinical study monitoring.

11.2 Auditing and Inspecting

The clinical study described herein is a pilot study intended to determine the level of ketosis (BHB) achievable with consumption of the food ingredient, (*R*)-1,3-Butanediol. The study is not being conducted in accordance with Good Clinical Practice, is not a regulated pharmaceutical trial, and therefore, will not be audited or inspected.

12 Ethical Considerations

This protocol and any amendments will be submitted to a properly constituted independent Ethics Committee (EC) or IRB, in agreement with local legal prescriptions, for formal approval of the study conduct. The decision of the EC/IRB concerning the conduct of the study will be made in writing.

All subjects for this study will be provided a consent form describing this study and providing sufficient information for subjects to make an informed decision about their participation in this study. This consent form will be submitted with the protocol for review and approval by the EC/IRB for the study. The formal consent of a subject, using the EC/IRB-approved consent form, must be obtained before that subject undergoes any study procedure. The consent form must be signed by the subject or legally acceptable surrogate.

The subjects for the study proposed herein are being recruited from the pool of employees at Genomatica. Participation in the study is not a requirement of employment, and measures are being taken to ensure that Genomatica employees do not feel coerced to partake in the study. For example, employees will not be directly solicited to enroll in research, neither orally nor through individual mailings or individual e-mails. Acceptable methods of recruitment will include flyers and other recruiting materials (approved by an IRB), displayed in the workplace where public announcements are permitted and/or mass e-mailers. The IRB will be provided with specific plans for ensuring the privacy of employees that participate in research. Also, policies will be clearly spelled out in the informed consent for issues such as injury or sickness as a result of the research. It will be made clear to employees that an employee's decision about research participation will not affect (favorably or unfavorably) performance evaluations, career advancement, or other employment-related decisions made by peers or supervisors.

13 Study Finances

13.1 Funding Source

This study will be financed by Genomatica Inc.

Appendix A Screen Captures of Online Screening Survey

Appendix B Detailed Instructions for Participants

B-1 Detailed instructions for participants

Day prior to study start

1. Final meal should be consumed to ensure a minimum of a **12-hour fast** prior to study start. You are permitted to drink water when you wake up; do not consume any food. Record the time at which the last meal was consumed using the online portal.
2. Place Avela™ test beverages in the fridge for consumption of chilled beverages on study date.
3. Download the Keto-Mojo App from the Apple Store or Google Play and make sure it is paired with your Keto-Mojo Monitor.
4. You will be sent a request on your App to join the study account, in order to share all BHB readings acquired during the study; please accept.
5. Test blood BHB levels
 - Use the Keto-Mojo monitor to measure your blood BHB level. The manual provided with the monitor provides step by step instructions. Alternatively, you can review these videos for assistance:
 - How to take a reading on the Keto-Mojo meter: <https://keto-mojo.com/video/gkplus-meter-testing-demo/>
 - How to use the lancet device: <https://keto-mojo.com/video/gkplus-meter-lancet-device/>

Study Start

6. Please ensure 12 hours have elapsed since the last food product was consumed.
7. Retrieve from the fridge the bottles of water containing the premixed Avela™ product.
8. On the day of study, if you are a female and you answered “no” to both of these questions during the study screening:
 - i. “If you are a female, are you post-menopausal, defined as not having had a period for 12 consecutive months or longer?” and
 - ii. “If you are a female, have you had any procedure that would result in you not being able to have children, such as “tying of tubes” or a removal of your ovaries?”

Take the pregnancy test provided prior to study start. Proceed with the study only if the test is negative (the result of the test will be included on the online portal).

Baseline (0 minutes)

9. Using the online portal, complete the mVAS for GI symptoms, followed by the SSS.
10. The on-screen timer will start automatically upon reading the welcome screen and completing age, height, last meal questions.
11. Use the Keto-Mojo monitor to measure your blood BHB level and record this value on the online portal.
12. **Consume one of the Avela™ beverages within 5 minutes.**

30 minutes

13. Using the online portal, complete the mVAS for GI symptoms, followed by the SSS.
14. Use the Keto-Mojo monitor to measure your blood BHB level and record this value on the online portal.
15. **Consume one of the Avela™ beverages within 5 minutes.**

60 minutes

16. Using the online portal, complete the mVAS for GI symptoms, followed by the SSS.
17. Use the Keto-Mojo monitor to measure your blood BHB level and record this value on the online portal.
18. **Consume one of the Avela™ beverages within 5 minutes.**

90 minutes

19. Using the online portal, complete the mVAS for GI symptoms, followed by the SSS.
20. Use the Keto-Mojo monitor to measure your blood BHB level and record this value on the online portal.

120 minutes

21. Using the online portal, complete the mVAS for GI symptoms, followed by the SSS.
22. Use the Keto-Mojo monitor to measure your blood BHB level and record this value on the online portal.

180 minutes

23. Using the online portal, complete the mVAS for GI symptoms, followed by the SSS.
24. Use the Keto-Mojo monitor to measure your blood BHB level and record this value on the online portal.

240 minutes

25. Using the online portal, complete the mVAS for GI symptoms, followed by the SSS.
26. Use the Keto-Mojo monitor to measure your blood BHB level and record this value on the online portal.
27. Consume the ALOHA Bar that has been provided, within a 7-minute timeframe.

300 minutes

28. Using the online portal, complete the mVAS for GI symptoms, followed by the SSS.
29. Use the Keto-Mojo monitor to measure your blood BHB level and record this value on the online portal.

Congratulations! You have now completed the study! Please open the Keto-Mojo App to allow it to sync with the Keto-Mojo Monitor and mail back the sharps container using the prepaid outer shipping carton, when convenient.

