On the day of the clinical study, subjects will follow instructions for study methodology (**Appendix B**). Subjects, who will have fasted overnight for 12 hours, will self-assess and record GI symptomology [using the modified visual analogue scale (mVAS) GI symptoms tool], alertness [using the Stanford Sleepiness Scale (SSS)], and blood BHB level (using the Keto Mojo BHB monitor), at time 0 minutes, as baseline measures, using an online study portal (**Appendix C**). Subjects will then consume 3 servings of Avela™, each providing 11.5 g of (R)-1,3-butanediol, with the first serving consumed at 0 minutes, the second serving at 30 minutes, and the third serving at 60 minutes. After the collection of baseline measures (at 0 minutes), GI symptomology (assessed using the mVAS GI symptoms tool), alertness (assessed using the SSS), and blood BHB levels (using the Keto Mojo BHB monitor) will be assessed, again, at 30, 60, 90, 120, 180, 240, and 300 minutes. At each time point, it is important that the order of collection be maintained [*i.e.*, 1. GI symptomology; 2. Alertness/sleepiness; 3. BHB level; and 4. Avela™ (when Avela™ is to be consumed; *i.e.*, at 0, 30, and 60 minutes)]. After the assessments at 240 minutes are complete, subjects will consume 1 ALOHA Organic Plant Based Protein Bar (Caramel Sea Salt). During the study, subjects will be asked to record their blood BHB levels and questionnaire results using the online portal (**Appendix C**). The results will be recorded electronically, using a de-identified survey on Survey Monkey, designed to protect subject anonymity [*i.e.*, the survey will not be affiliated with a name or any personal information; rather, each participant will have a unique identification number, which will be used to access the survey and upload the results of the study).

Number of Subjects	Investigational Product; Dose
30 subjects (males and females)	(R)-1,3-butanediol; 3 doses of 11.5 g/dose

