4.3 Inclusion Criteria

- Males and females, 18 to 65 years of age
- BMI 18 to <35.0 kg/m², inclusive
- Weight is ≥ 110 lbs
- Subject is judged to be in good health on the basis of medical history
- Subject is willing to fast overnight, prior to study start
- Subject is willing to avoid alcohol and intense physical activity the day prior to and on the day of testing
- Subject is capable of giving informed consent and complying with all study procedures/ requirements.

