4.4 Exclusion Criteria

- Previous GI disorders (e.g., inflammatory bowel disease, irritable bowel syndrome, history of surgery for weight loss, or gastroparesis)
- Gastroenteritis in the 2 weeks preceding the study
- Weight <110 lbs
- Diabetes
- History of alcohol or drug abuse
- Previous diagnosis of neurological disorders, depression, or mental illness with psychosis
- Unexplained alarm features (i.e., unintentional weight loss >10% body weight in the last 3 months, fevers, or blood in stools)
- Use of an antibiotic or any medication impacting gut transit during the 2 weeks before the study
- Constipation or diarrhea (defined as, on average, less than 3 stools per week or more than 3 stools per day, respectively)
- Allergy to tree nuts
- Women who are pregnant or breastfeeding;
- Persons with medical conditions affecting the pancreas, liver, thyroid, or gall bladder.

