4.6 Early Withdrawal of Subjects

4.6.1 When and How to Withdraw Subjects

Subjects may withdraw consent or be removed from the study by the Principal Investigator (PI). In the event that a subject is withdrawn from the study, the reason for the withdrawal will be documented, with the primary reason selected from the following standard categories:

- Withdrawal of consent: the subject requests to withdraw from further participation in the study in the absence of a medical need to withdraw as determined by the PI.
- Lost to follow-up: for unknown reasons, the subject did not upload their study results on to the electronic platform.
- Poor compliance: the subject consumes only 1 or 2 of the 3 servings of the study product; is found to meet an exclusionary criterion; and/or is not complying with other study obligations.
- AE: in the judgment of the PI and in the best interests of the subject, events that require discontinuation of study product (includes all categories of study product relatedness: None, Remote, Possible, Probable, or Highly Probable).
- Death: death of the subject.
- Other: causes of premature termination from the study other than the above, such as theft or loss of study products, termination of study by Sponsor, *etc.*

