5.2 Method for Assigning Subjects to Treatment Groups

All subjects included in the study will be assigned to receive the active investigational product [Avela™ (R)-1,3-butanediol] (*i.e.*, there is only one group for the study, with a before, after study design). Upon enrolment, each participant will be provided with a unique identification number.

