7.1 Clinical Evaluations

There are no clinical evaluations to be completed as part of this study protocol.

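### Does the absence of a written test-day entry for body weight undermine the results of this fixed-intake pilot?

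*Combined protocol and SAP*

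**What the plan says.** Weight enters the protocol in two ways.

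- **Eligibility.** Section 4.3 requires "Weight is ≥ 110 lbs" and section 4.4 excludes "Weight <110 lbs". Section 4.3 also limits BMI to 18 to <35 kg/m². Sections 5.1 and 6.1 have eligibility decided from the online screening survey, which Table 5.1-1 places up to 7 days before the test day.
- **Intake.** Sections 1.3 and 1.5 give 11.5 to 34.5 g/day the equivalent of 0.16 to 0.49 g/kg/day. The study intake itself is fixed at three servings of 11.5 g.

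On the test day, section 6.2.2 lists the last-meal time, the start time, the GI tool, the sleepiness scale, the BHB reading and the product. Appendix B, step 10, says the on-screen timer starts "upon reading the welcome screen and completing age, height, last meal questions". The kit in section 5.5.1 has a measuring tape and no scale, and section 7.1 says: "There are no clinical evaluations to be completed as part of this study protocol".

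On linkage, section 3.1 says of the results survey that "the survey will not be affiliated with a name or any personal information; rather, each participant will have a unique identification number" will be used, and section 5.2 says: "Upon enrolment, each participant will be provided with a unique identification number". Section 10.2 gives as examples of source data "consent forms and the online study portal data (blood BHB levels and questionnaires". Section 5.5.2 has the PI keep records of delivery and use for each subject, including the subjects' code numbers.

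**The concern.** Read together, these sections suggest that weight is needed but never captured with the results. The portal asks for height but apparently not weight. The survey that must deal with weight is completed before a participant number exists, and it is not named among the source-data examples. Section 8 leaves the analyses to the data management team, so no listed baseline table fills the gap.

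If weight were lost, the report could not give weight, BMI or intake per kilogram for the 30 participants. In a single-arm study a reader relies on the description of the sample to judge how far a BHB level applies elsewhere. A light sample and a strong response could look alike, and nobody could see whether GI symptoms fell mainly in lighter people. It might also seem that the 110 lb limit could not be verified, although section 4.6.1 allows removal of a subject who "is found to meet an exclusionary criterion".

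**Working it through.** **1. The protocol's own figure.** Dividing the gram intakes in section 1.3 by 70 kg, the reference weight used in section 1.4:

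- 11.5 / 70 = 0.164 g/kg
- 34.5 / 70 = 0.493 g/kg

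These round to the stated 0.16 and 0.49. The range is therefore a conversion at about 70 kg, although sections 1.3 and 1.5 do not say so.

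**2. Intake per kilogram at the weight limit.** 110 lb × 0.4536 = 49.9 kg.

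- Total: 34.5 / 49.9 = 0.69 g/kg
- One serving: 11.5 / 49.9 = 0.23 g/kg

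The gram limits in section 1.3 (up to 11.5 g per serving, up to 3 servings per day) are met whatever the participant weighs.

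**3. Can height replace weight?** At a given height, weight is BMI × height², so the BMI limits allow a range of 35 / 18 = 1.94-fold wherever the 110 lb limit does not bind. The heights below are illustrative.

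| Height | Lowest weight | Highest weight | 34.5 g per kg |
|---|---|---|---|
| 1.60 m | 49.9 kg (110 lb limit; 18 × 2.56 = 46.1 is below it) | 35 × 2.56 = 89.6 kg | 0.69 to 0.385 |
| 1.75 m | 18 × 3.0625 = 55.1 kg | 35 × 3.0625 = 107.2 kg | 0.63 to 0.32 |

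Height alone does not give intake per kilogram. That part of the concern is correct.

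**4. Could weight move the BHB result?** This can only be explored with assumed inputs. Suppose expected BHB varies with (g/kg) to a power of 0.5 to 1, and compare samples averaging 65 and 85 kg.

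- Ratio of intakes per kilogram: 85 / 65 = 1.308, a 31% difference at power 1
- √1.308 = 1.144, a 14% difference at power 0.5
- At power 0, no difference

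With an assumed between-person CV of 30 to 60%, the standard error of the mean at n = 30 is 30 / √30 = 5.5% to 60 / √30 = 11.0%. The power, the CV and both mean weights are assumptions, and the trial has no second sample. The calculation shows why weight is useful to describe. It does not show an error in the planned result.

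**5. How complete are the written lists?** Section 6.2.2 omits the age and height questions that Appendix B reports. The Appendix B steps omit the entry of the start time that section 6.2.2 requires. Table 5.1-1 shows none of these items. Step 10 exists to say when the timer starts, not to catalogue the portal's fields. No single list is exhaustive, so a missing item is weak evidence that the portal does not ask for it.

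**6. Eligibility and linkage.** Applying the 110 lb and BMI limits at screening requires weight information at that point, so showing that the limits were met is a task for the screening record. Several steps imply that staff can connect a participant with the screening answers and the code number: the delivery and use records in section 5.5.2; the test-day pregnancy test in section 6.2.1, which depends on screening answers; and the coordinator's app request and download of each subject's readings, also in 6.2.1. Section 3.1's exclusion of personal information evidently does not bar body measurements, since the portal takes age and height.

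**The case for a change.** The strongest case for a change is this. Asking for height without weight looks like an oversight, because height has little use here without it. The tolerability argument in section 1.5 depends on weight conversion: its 35 and 49 g/day equal 0.5 × 70 and 0.7 × 70, so a comparison with those studies on their own scale needs participants' weights. The survey could hold only a yes/no answer on the 110 lb limit. No sentence says that a weight value passes from the survey to the results, and one sentence or one question would settle it.

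Part of this stands. The visible text does not state that a numeric weight is stored against the participant number, and the linkage in the last step of the check is inferred. The stronger claims do not stand. Nothing shows that the 110 lb limit would go unverified, because it is applied at screening and section 10.2 lists examples only. Nor does anything show that weight could not be added to the results later, given the code-numbered records in section 5.5.2. The comparison with earlier studies is background; no objective in section 2 and no endpoint in section 3.2 is per kilogram.

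**Conclusion.** No change to the plan is called for. The missing statement is a detail that the data management team can settle when it prepares the baseline table, by taking weight from the screening record or from the portal if it is asked there. The primary BHB measurements and the GI and sleepiness scores are defined at a fixed 34.5 g, and recording weight would alter none of them. The most that could be lost is description: weight, BMI and g/kg for 30 people, with g/kg spanning about 0.32 to 0.63 at a height of 1.75 m and reaching 0.69 at the 110 lb limit. The 14 to 31% shift in expected BHB rests wholly on assumed inputs and carries no weight in this conclusion.

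The conclusion assumes that the screening survey, whose screens are not shown, keeps a usable weight value. If it kept only a yes/no answer and the portal asked nothing more, the baseline description would be poorer, but the fixed-intake results would still stand.

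Two wording points are separate from this one. The 70-kg reference behind 0.16 to 0.49 g/kg is unstated in sections 1.3 and 1.5. Section 1.4 describes the cycling study's intake once as 0.35 g/kg in two divided doses and once as a split dose totalling 0.7 g/kg; those passages must be reconciled before any per-kilogram comparison.
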